### ***Video Evaluation Questionnaires***

Staff experiences with viewing patient videos will be captured using a short **video evaluation questionnaire**. The direct care team will be encouraged to complete a video evaluation questionnaire for each video they have viewed. The questionnaire consists of seven closed-ended, multiple-choice questions with space for free-text comments. The questionnaire is anonymous and takes less than five minutes to complete. The questionnaire will be administered using a combination of methods to encourage a good response rate among busy clinical professionals. The questionnaire will be available to complete electronically, via Isla's platform, each time a member of staff views a patient video. Paper-based copies of the questionnaire will also be distributed to the direct care team to complete during 'downtime' periods – e.g. whilst awaiting handover or whilst awaiting meetings/ward round to begin. The paper-based video evaluation questionnaires will be administered by the researcher or by the clinical lead. Completed paper-based questionnaires will be placed in an envelope to preserve respondents' anonymity. At the end of the 3-month pilot, all questionnaire data will be transferred to an Excel file and stored in Imperial College Healthcare NHS Trust's Clinical, Analytics, Research and Evaluation (iCARE) informatics environment.

### ***Interviews with patients & carers***

The researcher will conduct semi-structured interviews with patients/ patients-carer dyads at or within two weeks of hospital discharge, or within 2 weeks of the end of the Isla pilot, whichever is sooner. The main aim of these interviews is to understand patients' experiences of being video recorded. Interviews will take place on the ward if the patient is still an inpatient, or over the telephone/Microsoft Teams/Zoom, according to the patient/carer's preferences if the patient has already been discharged. Written consent for interview will have been taken during the enrolment phase. However, due to the potential for fluctuating capacity in this patient group, the researcher will review the patient's capacity before the interview and conduct a further MCA, if appropriate. The patient and the carer will be asked to verbally confirm their consent, and this will be audio-recorded at the start of the interview. If the patient lacks capacity to consent, the researcher will

seek advice from the carer (as consultee) about whether the patient would want to go ahead with the interview; the carer/consultee's advice will be respected.

Interviews will follow the **patient/carer interview topic guide** and will last approximately 30 minutes. The researcher will adapt her language and use visual aids appropriate to the patient's level of understanding to enable patients with cognitive impairment to participate. Interviews will be audio-recorded and professionally transcribed. Any names/identifiers will be replaced with pseudonyms during the transcription process. Transcripts will be transferred to, and stored in, Imperial College Healthcare NHS Trust's Clinical, Analytics, Research and Evaluation (iCARE) informatics environment.

#### ***Interviews with ward staff***

The researcher will undertake semi-structured interviews with consenting members of the patient's direct care team during a 2-month period following the pilot of Isla's platform in the Medicine for the Elderly ward. The interviews will explore staff experiences with Isla's visual patient record platform and impacts of the platform on patient assessment & clinical decision-making, team communication, and care delivery. Permission will be sought from the ward manager/Consultant in charge to release individual staff members for interview. Interviews will take place in a meeting room on or near to the ward, or over the telephone/ Microsoft Teams/ Zoom according to the interviewee's preference. Written consent for the interviews will be taken and a study identifier will be assigned. Interviews will follow the **interview topic guide for ward staff** and will last approximately 30 minutes. Interviews will be audio-recorded and professionally transcribed. Any names/identifiers will be replaced with pseudonyms during the transcription process. Transcripts will be transferred to, and stored in, Imperial College Healthcare NHS Trust's Clinical, Analytics, Research and Evaluation (iCARE) informatics environment.

#### ***Video View Metrics***

At the end of the 3-month pilot of Isla's platform, video view metrics will be exported from Isla's audit log. Prior to storing the spreadsheet for descriptive analysis, the audit log will be pseudonymised by replacing the patient's name with their study ID and the names of the clinical staff who viewed the videos will be removed. The video view metrics spreadsheet will be transferred to, and stored in, Imperial College Healthcare NHS Trust's Clinical, Analytics, Research and Evaluation (iCARE) informatics environment.

## **11. END OF STUDY**

The end of study will be the last date of data collection – i.e. the date of the last interview with a study participant; this will take place within two months of the end of the pilot of Isla's visual patient record platform in the study setting. Thereafter, the research team will undertake data analysis and dissemination of the study findings (months 8 – 17). There will be no patient/participant follow up.

#### **CRITERIA FOR ELECTIVELY STOPPING THE STUDY PREMATURELY:**

In the unlikely event that there is a security incident (data leak, cyber security incident) that impacts on Isla's visual record platform, the study will be stopped pending investigation of the incident and return to normal operations.

## 12. DATA ANALYSIS

Table 1 (pages 19-20) summarises the outcomes of interest, measures/approaches, and methods of data analysis.

As this is a feasibility study, quantitative analyses will be primarily descriptive. Counts and percentages will be calculated for categorical variables; means and standard deviations (SD) will be calculated for continuous variables.

Analyses of qualitative data (Video Evaluation Questionnaire - free-text responses; interview transcripts) will be undertaken using the Framework method developed by Ritchie & Spencer. Sekhon's *Theoretical Framework of Acceptability of Healthcare Interventions* will provide *a priori* themes as part of the framework for analysis of direct care team interview transcripts; themes emerging from the data itself will be added to the framework during the analytical process.

The theoretical framework of acceptability consists of seven component constructs: affective attitude, burden, perceived effectiveness, ethicality, intervention coherence, opportunity costs, and self-efficacy. These are defined further below:

- Affective Attitude: How an individual feels about the intervention
- Burden: The amount of effort required to participate in the intervention
- Ethicality: The extent to which the intervention has a good fit with an individual's value system
- Intervention Coherence: The extent to which the participant understands the intervention and how it works
- Opportunity Costs: The extent to which benefits, profits, or values must be given up to engage in the intervention
- Perceived Effectiveness: The extent to which the intervention is perceived to achieve its purpose
- Self-efficacy: The participant's confidence that they can perform the behaviour(s) required to participate in the intervention

## 13. ADVERSE EVENTS

Staff witnessing any behaviour on a patient videorecording that is cause for concern should report their concerns immediately to the clinical lead [name], either in person or via email [[contact]](mailto:[contact]). Alternatively, [name] (Matron – Medicine for the Elderly) [[contact]](mailto:[contact]), or [name] (Ward Manager – Medicine for the Elderly) [[contact]](mailto:[contact]), may be contacted.

**A Security Incident** is any incident that occurs by accident or deliberately that impacts Isla's users or the patient data on the system. This could be anything that threatens the confidentiality, integrity or availability of information, data or services delivered by Isla. This includes unauthorised access to, use, disclosure, modification, or destruction of data or services used or provided by Isla. In the unlikely event that there is a security incident, the study will be stopped pending investigation of the incident and return to normal operations.

## DEFINITIONS

**Adverse Event (AE):** any untoward medical occurrence in a patient or clinical study subject.

**Serious Adverse Event (SAE):** any untoward medical occurrence or effect that:

- **Results in death**
- **Is life-threatening** – *refers to an event in which the subject was at risk of death at the time of the event; it does not refer to an event which hypothetically might have caused death if it were more severe*
- **Requires hospitalisation, or prolongation of existing inpatients' hospitalisation**
- **Results in persistent or significant disability or incapacity**
- **Is a congenital anomaly or birth defect**

Medical judgement should be exercised in deciding whether an AE is serious in other situations. Important AEs that are not immediately life-threatening or do not result in death or hospitalisation but may jeopardise the subject or may require intervention to prevent one of the other outcomes listed in the definition above, should also be considered serious.

## REPORTING PROCEDURES

All adverse events should be reported. Depending on the nature of the event the reporting procedures below should be followed. Any questions concerning adverse event reporting should be directed to the Chief Investigator in the first instance.

### 5.3.1 Non serious AEs

All such events, whether expected or not, should be recorded.

### 5.3.2 Serious AEs

An SAE form should be completed and emailed to the Chief Investigator within 24 hours. However, relapse and death due to frailty, and hospitalisations for elective treatment of a pre-existing condition do not need reporting as SAEs.

All SAEs should be reported to the South Central - Oxford C Research Ethics Committee where in the opinion of the Chief Investigator, the event was:

- 'related', ie resulted from the administration of any of the research procedures; and
- 'unexpected', ie an event that is not listed in the protocol as an expected occurrence

Reports of related and unexpected SAEs should be submitted within 15 days of the Chief Investigator becoming aware of the event, using the NRES SAE form for non-IMP studies. The Chief Investigator must also notify the Sponsor of all related and unexpected SAEs.

Local investigators should report any SAEs as required by their Local Research Ethics Committee, Sponsor and/or Research & Development Office.

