## *Where*

Patient videos will be recorded on the Medicine for the Elderly ward or in other areas within St. Mary's hospital where patients' functional abilities are assessed (e.g. hospital staircase, therapy kitchen; therapy gym).

Patient videos will be viewed on an ICHT password-protected computer on Trust premises.

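### The SAE exemption for deaths due to frailty has no relatedness condition, so such a death skips the Chief Investigator's assessment and has no stated reporting route

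*Protocol*

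**What the plan says.** Protocol section 13 sets out safety reporting in four steps.

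- **Definitions.** An event is serious if, among other criteria, it "Results in death".
- **Reporting procedures.** The general rule is "All adverse events should be reported", followed by "Depending on the nature of the event the reporting procedures below should be followed". Questions about reporting go first to the Chief Investigator.
- **Non serious AEs (numbered 5.3.1).** "All such events, whether expected or not, should be recorded". This covers non-serious events only.
- **Serious AEs (numbered 5.3.2).** "An SAE form should be completed and emailed to the Chief Investigator within 24 hours". An exception follows at once: "relapse and death due to frailty, and hospitalisations for elective treatment of a pre-existing condition do not need reporting as SAEs". An SAE goes to the ethics committee if the Chief Investigator considers it both unexpected and related, where related means that it "resulted from the administration of any of the research procedures". The sponsor is notified of the same events.

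Section 6 (Patients) requires each patient to be considered frail or pre-frail by the direct care team. Section 8 has that same team record the videos. The content may include mobility, transfers, and eating and drinking, and the locations may include the "hospital staircase, therapy kitchen; therapy gym".

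**The concern.** Exempting expected events from expedited reporting is common and acceptable. The difficulty is that this exemption is defined by cause alone and takes effect before the step at which the protocol has relatedness assessed. It carries no qualifier such as *unless possibly related to a research procedure*.

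The exempt cause is also close to the condition that brings patients into the study. Where every patient is frail or pre-frail, frailty is an easy attribution for a death after a decline in hospital, and the protocol does not say who makes that attribution, by what criteria, or where it is written down.

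Safety oversight is at stake, not an estimate. If a recorded task contributed to a death and the death was put down to frailty, no stated step would bring it to the Chief Investigator for a relatedness judgement, and the ethics committee and sponsor reports that depend on that judgement would not follow.

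The exemption also covers relapse, a term with no definition in the protocol and no evident meaning for frailty. Staff cannot apply it consistently.

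**Working it through.** The plan states no figure to reproduce on this point. The check follows one event through section 13: the death of a patient participant that someone attributes to frailty.

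1. **Is it serious?** Yes. Under Definitions, any event that results in death is an SAE.
2. **Does the non-serious route record it?** No. That subsection covers non-serious events only.
3. **Does the SAE route report it?** No. The exemption removes the need to report it as an SAE, and so the need for the form due to the Chief Investigator within 24 hours.
4. **Is relatedness assessed first?** Not by any stated step. The relatedness and expectedness judgement belongs to the Chief Investigator and concerns SAEs. The SAE form is the only stated reporting route by which an event reaches that person, and step 3 has removed it.
5. **Does another part of the protocol catch the death?**
   - Section 9 says that clinical outcomes are outside the scope of this study, so death is not collected as an outcome.
   - The cause-for-concern report in section 13 is for behaviour seen on a video.
   - The only criterion for stopping early in section 11 is a security incident.
   - The Screening/Enrolment Log records withdrawals, with no mention of deaths or their causes.
   - The Video Tracker (sections 8 and 10) records recording attempts and problems with them, but nothing links an entry to a later death or to a relatedness judgement.
6. **Would a death that did reach the Chief Investigator go further?** Possibly not. An event counts as unexpected if the protocol does not list it as an expected occurrence. There is no separate list of expected events, so the exemption is the nearest thing to one, and a death due to frailty could be read as expected.

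The result is that such a death has no stated route and no documented relatedness assessment.

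**Whom the exemption can concern.** The planned sample in sections 6 and 7 is 30 patients + 30 carers + 35 ward staff = 95.

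- Patients: 30/95 = 31.6%. All must be frail or pre-frail; the split between the two is not given.
- Carers and staff: 65/95 = 68.4%. They have no frailty criterion.

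The overlap between exempt cause and entry criterion therefore applies to all 30 patients, not to most of the 95 participants. Thirty is the number of people to whom the label could be applied. It does not estimate deaths or missed reports.

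**The case against.** Five counter-arguments deserve an answer.

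**The exemption is an explicit exception.** A reader might infer that the Serious AEs text flatly contradicts the rule that all adverse events be reported. The documents do not support that. The general rule points to the procedures below it, and the exemption is worded as an exception to SAE reporting. It does not say that these deaths go unrecorded. This stands: the fault is a missing route, not a contradiction.

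**Attribution is itself a judgement.** The wording covers death caused by frailty, not any death of a frail person, so someone must form a view on cause. It would be wrong to say that nobody makes a causal judgement. This too stands, but the person is unnamed, the judgement need not be documented, and it takes the place of the Chief Investigator's.

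**A fall or choking death is not exempt on a plain reading.** A death after an identifiable event during a recorded task would still need the SAE form. A reader might infer that the rule as written hides related deaths. It does so only if the death is misattributed. That limits the point but does not remove it, because the assessment that would reveal a misattribution is the one skipped.

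**Other safeguards exist.** Doubtful cases can be put to the Chief Investigator, the Video Tracker would plausibly show an incident during recording, and local investigators must report SAEs as their ethics committee, sponsor or R&D office requires. These help, but none is a relatedness check. The first depends on someone having a doubt, and the last on requirements that the protocol does not set out.

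**The added risk is low.** The staircase, kitchen and gym are places where function is assessed in any case, recordings last at most five minutes, and the videos run alongside usual care. The document does not separate the risk of the task from any risk added by filming. This is a fair reason to expect few related events. Whether a given event came from the study or from routine assessment is, however, exactly what the Chief Investigator is meant to decide.

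**Conclusion.** The point holds in a limited form. The protocol lets an unnamed person's attribution of a death to frailty replace the Chief Investigator's documented relatedness assessment, and it gives such deaths no stated reporting route. That is a flaw in a rule as written, not a detail left for another document.

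Its size cannot be calculated, because no expected number of deaths is given. No outcome analysis in section 12 depends on it. The document does not show that deaths related to video-recording are likely, or that any would be hidden. It shows that the procedure would not detect one misattributed to frailty.

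The conclusion rests on two assumptions: that the SAE form is the only reporting route to the Chief Investigator, as section 13 reads, and that no study document outside the protocol, such as a sponsor procedure, requires all deaths to be assessed. If one does, the protocol should refer to it and the point largely falls away. Otherwise the text should be changed; the change is worth making but does not call the study design into question.

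**What to change.** Reconcile the four parts of section 13 (Definitions, Reporting procedures, Non serious AEs, Serious AEs) as follows.

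- Apply the exemption only once the Chief Investigator, or a named delegate, has recorded that the event is unrelated to the research procedures. Until then the event follows the SAE route.
- State who may attribute a death to frailty and where that attribution is recorded.
- Keep a simple log of every patient death, with date, attributed cause, any recent recording, and the relatedness judgement.
- State whether an exempt event counts as expected, so that a related death is not withheld from the ethics committee on that ground alone.
- Define relapse for this population, or delete it.

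The cost is a few sentences in section 13 and a brief check and form for each patient death. With 30 patients on one ward over a 3-month pilot, the load should be small. The drawback is some extra paperwork for deaths that prove unrelated.

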## 14. REGULATORY ISSUES

### ETHICS APPROVAL

The Study Coordination Centre has obtained approval from the South Central - Oxford C Research Ethics Committee (23/SC/0167) (REC) and Health Research Authority (HRA). The study must also receive confirmation of capacity and capability from each participating NHS Trust before accepting participants into the study or any research activity is carried out. The study will be conducted in accordance with the recommendations for physicians involved in research on human subjects adopted by the 18th World Medical Assembly, Helsinki 1964 and later revisions.

### CONSENT

Consent to enter the study, including enrolment procedures for adults lacking capacity to consent, is outlined in section 7 of this protocol. Consent to enter the study must be sought from each participant only after a full explanation has been given, an information leaflet offered and time allowed for consideration. Signed participant consent or a signed consultee declaration form will be obtained. The right of the participant to refuse to participate without giving reasons will be respected. All participants are free to withdraw at any time from the protocol treatment without giving reasons and without prejudicing further treatment.

### CONFIDENTIALITY

Isla's [privacy notice](#) outlines how Isla protects patients' privacy in their role as data processor, on behalf of Imperial College Healthcare NHS Trust as data controller.

Research data will be anonymous or pseudonymised, as per section 10 of this protocol.

All research data will be transferred to, and stored in, Imperial College Healthcare NHS Trust's Clinical, Analytics, Research and Evaluation (iCARE) informatics environment. iCARE is a secure NHS

based platform. The research team will access the data in the NHS platform, meaning the data does not leave the NHS. All access to the data is audited and controlled within the NHS. Data and all appropriate documentation will be stored for a minimum of 5 years after the completion of the study.

The Chief Investigator will preserve the confidentiality of participants taking part in the study and is registered under the Data Protection Act.

## INDEMNITY

Imperial College Healthcare NHS Trust holds standard NHS Hospital Indemnity and insurance cover with NHS Resolution for NHS Trusts in England, which apply to this study.

## SPONSOR

Imperial College Healthcare NHS trust will act as the main Sponsor for this study. Delegated responsibilities will be assigned to the NHS trust taking part in this study.

## FUNDING

NIHR and HEE are funding this study. NHS support costs are covered; however, study participants will not receive payment.

## AUDITS

The study may be subject to audit by Imperial College Healthcare NHS Trust under their remit as sponsor and other regulatory bodies to ensure adherence to GCP and the UK Policy Framework for Health and Social Care Research.

## 15. STUDY MANAGEMENT

The day-to-day management of the study will be co-ordinated by [name] (Chief Investigator), [name] (ICHT Transformation Chief Clinical Information Officer) and [name] (Clinical Lead), working closely with the direct care team on the Medicine for the Elderly ward.

[name] will be responsible for liaising with Isla (named contact: [name] – Technical Programme Manager), the ICHT IT Project Manager for Isla ([name]), and with the study sponsor (Imperial College Healthcare NHS Trust).

## 16. PUBLICATION POLICY

Key audiences likely to benefit from hearing about our findings are:

- A. Professionals involved in assessing/caring for older people with frailty

- B. Patients and carers
- C. Academia

We will use multiple vehicles for dissemination, including:

- Presentations at the British Geriatrics Society Autumn meeting (Nov-2024) and the International Society for Quality in Healthcare conference (Oct-2024) (A).
- Peer-reviewed publications – target journal: *Age & Ageing* (A&C).
- Visual/lay summaries for patient/carer participants, disseminated to the public via local NHS newsletters and national patient-facing organisations (Carers UK/National Voices) (B).
- An internal report and workshops/meetings with Imperial College Healthcare NHS Trust staff
  - Online press releases/social media, using existing networks/NIHR infrastructure to broaden dissemination and increase awareness (A-C).

